4.4 Medical validation of programmed overall lesion response

In order to be as objective as possible the RECIST programmed calculated response assessment is very strict regarding measurement methods (i.e. any assessment with more or less sensitive method than the one used to assess the lesion at baseline is considered UNK) and not available evaluations (i.e. if any target or non-target lesion was not evaluated the whole overall lesion response is UNK unless remaining lesions qualified for PD). This contrasts with the slightly

more flexible guidance given to local investigators (and to the central reviewers) to use expert judgment in determining response in these type of situations, and therefore as a consequence discrepancies between the different sources of response assessment often arise. To ensure the quality of response assessments from the local site and/or the central reviewer, the responses may be re-evaluated by clinicians (based on local investigator data recorded in eCRF or based on central reviewer data entered in the database) at Novartis or external experts. In addition, data review reports will be available to identify assessments for which the investigators' or central reader's opinion does not match the programmed calculated response based on RECIST criteria. This may be queried for clarification. However, the investigator or central reader's response assessment will never be overruled.

If Novartis elect to invalidate an overall lesion response as evaluated by the investigator or central reader upon internal or external review of the data, the calculated overall lesion response at that specific assessment is to be kept in a dataset. This must be clearly documented in the RAP documentation and agreed before database lock. This dataset should be created and stored as part of the 'raw' data.

Any discontinuation due to 'Disease progression' without documentation of progression by RECIST criteria should be carefully reviewed. Only patients with documented deterioration of symptoms indicative of progression of disease should have this reason for discontinuation of treatment or study evaluation.

4.5 Programming rules

The following should be used for programming of efficacy results:

4.5.1 Calculation of 'time to event' variables

Time to event = end date - start date + 1 (in days)

[figure not shown]
When no post-baseline tumor assessments are available, the date of randomization/start of treatment will be used as end date (duration = 1 day) when time is to be censored at last tumor assessment, i.e. time to event variables can never be negative.

4.5.2 Incomplete assessment dates

All investigation dates (e.g. X-ray, CT scan) must be completed with day, month and year.

If one or more investigation dates are incomplete but other investigation dates are available, this/these incomplete date(s) are not considered for calculation of the assessment date (and assessment date is calculated as outlined in [Section 3.2.7](#)). If all measurement dates have no day recorded, the 1st of the month is used.

If the month is not completed, for any of the investigations, the respective assessment will be considered to be at the date which is exactly between previous and following assessment. If a previous and following assessment is not available, this assessment will not be used for any calculation.

4.5.3 Incomplete dates for last known date patient alive or death

All dates must be completed with day, month and year. If the day is missing, the 15th of the month will be used for incomplete death dates or dates of last contact.

4.5.4 Non-target lesion response

If no non-target lesions are identified at baseline (and therefore not followed throughout the study), the non-target lesion response at each assessment will be considered 'not applicable (NA)'.

4.5.5 Study/project specific programming

The standard analysis programs need to be adapted for each study/project.

4.5.6 Censoring reason

In order to summarize the various reasons for censoring, the following categories will be calculated for each time to event variable based on the treatment completion page, the study evaluation completion page and the survival page.

For survival the following censoring reasons are possible:

- Alive
- Lost to follow-up

For PFS and TTP (and therefore duration of responses) the following censoring reasons are possible:

- Ongoing without event
- Lost to follow-up
- Withdrew consent
- Adequate assessment no longer available*
- Event documented after two or more missing tumor assessments (optional, see [Table 3-2](#))
- Death due to reason other than underlying cancer (only used for TTP and duration of response)
- Initiation of new anti-cancer therapy

* Adequate assessment is defined in [Section 3.2.7](#). This reason is applicable when adequate evaluations are missing for a specified period prior to data cut-off (or prior to any other censoring reason) corresponding to the unavailability of two or more planned tumor assessments prior to the cut-off date. The following clarifications concerning this reason should also be noted:

- This may be when there has been a definite decision to stop evaluation (e.g. reason="sponsor decision" on study evaluation completion page), when patients are not followed for progression after treatment completion or when only UNK assessments are available just prior to data cut-off).
- The reason "Adequate assessment no longer available" also prevails in situations when another censoring reason (e.g. withdrawal of consent, loss to follow-up or alternative anti-

cancer therapy) has occurred more than the specified period following the last adequate assessment.

- This reason will also be used to censor in case of no baseline assessment.

14.2 Appendix 2: irRECIST

1 Introduction

Immune-related response criteria have been developed to better assess the patterns of response and progression with cancer immunotherapies (Wolchok et al. 2009, Nishino et al. 2013, 2014). This document outlines the working definitions and rules for immune-related response criteria based on RECIST 1.1 (irRECIST).

For definition of measurable and non-measurable lesions, methods of tumor measurement, baseline documentation of target and non-target lesions, eligibility based on measurable disease, follow-up evaluation of lesions, etc., refer to RECIST 1.1 (Appendix 1).

2 Baseline assessment of tumor burden

All measurable lesions (nodal and non-nodal) up to a maximum of five lesions in total (and a maximum of two lesions per organ), representative of all involved organs should be identified as target lesions and recorded and measured at baseline. All other lesions present at baseline will be considered as non-target lesions. Together these present the baseline tumor burden.

The Total Measurable Tumor Burden (TMTB) at baseline is defined as the sum of diameters (SOD) of all target lesions.

3 Post-baseline assessment of tumor burden

Target, non-target and new lesions (measurable and non-measurable) will be evaluated at each post-baseline assessment. Target and non-target lesions identified at baseline will continue to be followed as target and non-target lesions, respectively. New measurable lesions will be included in the TMTB which is defined as the SOD of target lesions and the new measurable lesions for post-baseline assessments. The nadir TMTB at a given time point 'n' is defined as the smallest TMTB observed for a given patient up to, but excluding that time point (i.e. from baseline to timepoint 'n-1').

A new measurable lesion is a newly observed lesion that was not present at baseline tumor assessment and is measurable as per RECIST 1.1. Overall a maximum of five new measurable lesions (nodal or non-nodal) can be included in the TMTB with a maximum of two new measurable lesions per organ. If there are more than 5 new measurable lesions in total, or more than 2 in the same organ at a post-baseline tumor evaluation, then the largest and most reproducible new measurable lesions should be included in TMTB. Note that two new measurable lesions per organ can be included in the TMTB irrespective of whether baseline target lesions were already identified in that organ or not. All other new lesions will be included in the overall tumor burden assessment as new non-measurable lesions.

A new measurable lesion included in the TMTB must always be included in TMTB for all subsequent tumor assessments. A new non-measurable lesion will always be followed as a non-measurable lesion at subsequent tumor assessments even if it becomes measurable.

The overall tumor burden (OTB) includes the TMTB, non-target lesions and new non-measurable lesions.

4 Overall response assessment

An overall response assessment should occur at each post-baseline assessment, and will take into account the evaluation of the TMTB together with the status of non-target lesions and new non-measurable lesions.

Baseline non-target lesions

The response of non-target lesions primarily contributes to the overall response assessment of complete response (irCR), with persisting non-target lesions preventing irCR. Only a clear and unequivocal worsening of non-target lesions alone (i.e. worsening of the tumor burden which is substantial enough leading to discontinuation or change of therapy), would be indicative of irPD.

New lesions

A new lesion does not automatically indicate progressive disease.

New measurable lesions are added to the SOD to obtain the TMTB as described in Section 14.2.3 at each post-baseline tumor evaluation. All new lesions not selected as new measurable lesions for obtaining TMTB are considered as new non-measurable lesions and are followed qualitatively. Only an unequivocal progression of new non-measurable lesions (i.e. worsening of the overall tumor burden which is substantial enough leading to discontinuation or change of therapy) would be indicative of irPD. Persisting new non-measurable lesions prevent irCR.

Note: The designation of overall irPD solely on the basis of change in non-target disease or new non-measurable lesions in the face of no progression based on TMTB is expected to be uncommon.

4.1 Definition of response categories

The response categories at each post-baseline assessment are defined as follows:

- **Immune related Complete Response (irCR):** Complete disappearance of all measurable and non-measurable lesions. In addition, any pathological lymph nodes must have a reduction in short axis to < 10 mm.
 - TMTB may be greater than zero at the time of CR, if nodal lesions are included in TMTB.
 - In some circumstances it may be difficult to distinguish residual disease from normal tissue. When the evaluation of complete response depends on this determination, it is recommended that the residual lesion be investigated (fine needle aspirate/biopsy) to determine the irCR.
- **Immune related Partial Response (irPR):** At least 30% decrease in the TMTB compared to baseline and not qualifying for irPD or irCR
- **Immune related Progressive Disease (irPD):** At least a 20% increase in the TMTB compared to nadir. In addition to the relative increase of 20%, TMTB must also demonstrate an absolute increase of at least 5 mm. An unequivocal progression of existing non-target or new non-measurable lesions may also lead to irPD.

- **Immune related Stable Disease (irSD):** Neither a sufficient shrinkage to qualify for irPR or irCR, nor an increase in lesions, or a clear and unequivocal progression of existing non-target or new non-measurable lesions that would qualify for irPD.
 - **Unknown for irRECIST (irUNK):** Progression has not been documented and one or more target lesions or new measurable lesions observed at earlier assessment have not been assessed, or have been assessed using a significantly different method (i.e. prevents reasonable comparison to the prior assessments) than baseline (target lesions) or assessment of first occurrence (new measurable lesions). Note that if non-target or new non-measurable lesions have not been assessed at any given post-baseline time-point, then this will not lead to overall response irUNK. If the evaluation of any non-target lesion or new non-measurable lesion is not done, and all target lesions and other non-target lesions disappeared, irCR cannot be determined and overall response must be “irPR”.

Table 4-1 Overall response at each post-baseline assessment

Target and new measurable lesions based on (TMTB), * (%)	Non-target lesions and New non-measurable lesions	Overall lesion response
- 100 [a], [b]	Absent	irCR
- 100 [a], [b]	Stable/not evaluated	irPR
≤-30 [b]	Absent/Stable/not evaluated	irPR
>-30 [b] and < +20 [c]	Absent/Stable/not evaluated	irSD
≥+20 [c]	Any	irPD
Any	Unequivocal progression [e]	irPD

[a] TMTB may be greater than zero at the time of irCR, if nodal lesions are included in TMTB

[b] Compared to baseline

[c] Compared to nadir

[d] If worsening of non-target or new non-measurable lesions is substantial enough leading to discontinuation or change of treatment.

4.1.1 Notes on lesion response

Reappearance of lesions

If the lesion reappears at the same anatomical location where a target lesion had previously disappeared, it is advised that the time point of lesion disappearance (i.e., the “0 mm” recording) be re-evaluated to make sure that the lesion was not actually present and/or not visualized for technical reasons in this previous assessment. If the previous disappearance of the lesion is confirmed, then the investigator/radiologist has to decide between the following possibilities:

- The lesion is a new lesion, in which case the overall tumor assessment should consider this appropriately either as a new measurable or new non-measurable lesion.
- The lesion is clearly a reappearance of a previously disappeared lesion, in which case the size of the lesion has to be entered in the CRF and the tumor assessment will remain based on the sum of tumor measurements as presented in the Table above. This applies to patients who have not achieved target response of irCR. For patients who have achieved irCR, please refer to below.

Progressive disease after complete response

Similar to RECIST 1.1, following a confirmed irCR, an irPD can subsequently only be assigned if any one of below is observed:

- Either a non-nodal target or new-measurable lesion that disappeared earlier reappears at the same anatomical location.
- Any single nodal lesion gets >10mm in diameter and there is at least 20% increase in sum of the diameters of all nodal target and nodal new-measurable lesions relative to nadir with at least 5 mm increase in the absolute sum of the diameters.
- Unequivocal progression based on non-target and new non-measurable lesions.

Missing measurements

In cases where measurements are missing for one or more target or new-measurable lesions it is sometimes still possible to assign irPD based on the measurements of the remaining lesions. For example, if the sum of diameters for 5 target lesions at baseline is 100 mm at baseline and the sum of diameters for 3 of those lesions at a post-baseline visit is 140 mm (with data for 2 other lesions missing) then an irPD should be assigned. However, in other cases where an irPD cannot definitely be attributed, the target lesion response would be irUNK.

Nodal lesions

- Nodal lesion decrease to normal size: When nodal disease is included in the sum of target lesions and the nodes decrease to “normal” size they should still have a measurement recorded on scans. This measurement should be reported even when the nodes are normal in order not to overstate progression should it be based on increase in the size of nodes.
- The measurements for nodal lesions, even if less than 10 mm in size, will contribute to the calculation of target lesion response in the usual way with slight modifications.
- Since nodal lesions less than 10 mm are considered normal, an irCR for target lesion response based on TMTB should be assigned when all nodal target and new-measurable lesions shrink to less than 10 mm and all non-nodal target lesions have disappeared.

Splitting and coalescence of lesions

- Lesions split: In some circumstances, disease that is measurable as a target or new-measurable lesion at baseline and appears to be one mass can split to become two or more smaller sub-lesions at subsequent assessments. When this occurs, the diameters (long axis - non-nodal lesion, short axis - nodal lesions) of the two split lesions should be added together and the sum recorded in the diameter field on the case report form under the original lesion number. This value will be included in the sum of diameters when deriving target lesion response based on TMTB. The individual split lesions will not be considered as new lesions.
- Lesions coalesced: Conversely, it is also possible that two or more lesions which were distinctly separate at earlier assessment(s) become confluent at subsequent visits. When this occurs a plane between the original lesions may be maintained that would aid in obtaining diameter measurements of each individual lesion. If the lesions have truly coalesced such that they are no longer separable, the maximal diameters (long axis - non-nodal lesion, short axis - nodal lesions) of the “merged lesion” should be used when calculating the sum of diameters for target lesions. On the case report form, the diameter of the “merged lesion” should be recorded for the size of one of the original lesions while

a size of “0”mm should be entered for the remaining lesion numbers which have coalesced.

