- Lesions coalesced: Conversely, it is also possible that two or more lesions which were distinctly separate at baseline become confluent at subsequent visits. When this occurs a plane between the original lesions may be maintained that would aid in obtaining diameter measurements of each individual lesion. If the lesions have truly coalesced such that they are no longer separable, the maximal diameters (long axis - non-nodal lesion, short axis - nodal lesions) of the “merged lesion” should be used when calculating the sum of diameters for target lesions. On the case report form, the diameter of the “merged lesion” should be recorded for the size of one of the original lesions while a size of “0”mm should be entered for the remaining lesion numbers which have coalesced.
- The **measurements for nodal lesions**, even if less than 10 mm in size, will contribute to the calculation of target lesion response in the usual way with slight modifications.
- Since lesions less than 10 mm are considered normal, a CR for target lesion response should be assigned when all nodal target lesions shrink to less than 10 mm and all non-nodal target lesions have disappeared.
- Once a CR target lesion response has been assigned a CR will continue to be appropriate (in the absence of missing data) until progression of target lesions.
- Following a CR, a PD can subsequently only be assigned for target lesion response if either a non-nodal target lesion “reappears” or if any single nodal lesion is at least 10 mm

and there is at least 20% increase in sum of the diameters of all nodal target lesions relative to nadir with at least 5 mm increase in the absolute sum of the diameters.

- A change in method for the evaluation of one or more lesions will usually lead to an UNK target lesion response unless there is progression indicated by the remaining lesions which have been evaluated by the same method. In exceptional circumstances an investigator or central reviewer might over-rule this assignment to put a non-UNK response using expert judgment based on the available information. E.g. a change to a more sensitive method might indicate some tumor shrinkage of target lesions and definitely rule out progression in which case the investigator might assign an SD target lesion response; however, this should be done with caution and conservatively as the response categories have well defined criteria.

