4.3 Determination of Best overall response

For best overall response (BOR), in general all the details as specified in the RECIST 1.1 appendix Section 14.1.3.1 will apply unless stated otherwise below or in the study protocol.

The best overall response for each patient is determined from the sequence of overall responses according to the following rules:

- irCR = at least two determinations of irCR at least 4 weeks apart before confirmed progression. Note that there should not be any tumor assessment with an overall response of irPD in between
- irPR = at least two determinations of irPR or better at least 4 weeks apart before confirmed progression (and not qualifying for irCR). Note that there should not be any tumor assessment with an overall response of irPD in between
- irSD = at least one irSD assessment (or better) > 6 weeks after randomization/start of treatment and before confirmed progression (and not qualifying for irCR or irPR).
- irPD = confirmed immune related progression or immune related progression with no further adequate tumor assessments £ 12 weeks after randomization/ start of treatment (and not qualifying for irCR, irPR or irSD)
- irUNK = all other cases (i.e. not qualifying for confirmed irCR or irPR and without irSD after more than 6 weeks or early progression within the first 12 weeks)
- If the next tumor assessment is inadequate with an overall response of irUNK then the next adequate tumor assessment will be considered for confirmation. E.g. an irCR followed by irUNK followed by irPR will be a confirmed irPR.

Similar to RECIST 1.1 overall lesion response of irCR or irPR, after their confirmation, will remain the same or improve until confirmed irPD.

5 Only non-measurable disease at baseline

For patients with only non-measurable disease at baseline, unequivocal progression of non-target lesions (i.e. worsening of the overall tumor burden which is substantial enough leading to discontinuation or change of therapy) will constitute an irPD. In addition, the appearance of new lesions (measurable or non-measurable) consistent with unequivocal progression taking

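### Appendix 2 (irRECIST) gives two answers for a non-nodal measurable lesion that first appears after a confirmed irCR

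*Protocol*

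**What the plan says.** Appendix 2, Section 4.1.1 (progressive disease after complete response), states that "following a confirmed irCR, an irPD can subsequently only be assigned if any one of below is observed". The three listed events are:

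1. "Either a non-nodal target or new-measurable lesion that disappeared earlier reappears at the same anatomical location";
2. a node above 10 mm, with absolute growth of 5 mm or more, provided that "there is at least 20% increase in sum of the diameters of all nodal target and nodal new-measurable lesions relative to nadir";
3. unequivocal progression of non-target or new non-measurable disease.

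Section 4.3 adds that "overall lesion response of irCR or irPR, after their confirmation, will remain the same or improve until confirmed irPD".

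Other parts of the same appendix treat new lesions differently. Section 3 says "New measurable lesions will be included in the TMTB". Section 4.1 defines irPD as a TMTB rise over nadir of at least 20% and at least 5 mm, and Table 4-1 repeats the 20% criterion. Neither makes an exception for a patient already in irCR. Section 4.1 defines irCR as "Complete disappearance of all measurable and non-measurable lesions", with nodes below 10 mm.

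SAP 2.7.1 refers to the appendix for best overall response under irRECIST. SAP 5.5 covers only the confirmation of irPD calls already made.

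**The concern.** A non-nodal measurable metastasis first seen after a confirmed irCR does not match the list. It is not a reappearance at an earlier site, it is not nodal, and it is not non-measurable. Item 3 does not catch it either: under Sections 3 and 4, only new lesions not selected into TMTB count as new non-measurable, and the largest ones are selected. Read literally, a surplus smaller lesion could support irPD while the largest could not.

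Section 4.1.1 presents itself as parallel to RECIST 1.1, but the parallel is incomplete. In Appendix 1, Section 2.4.2, the restriction is that "a PD can subsequently only be assigned for target lesion response", and Section 2.4.4 makes any new lesion PD by a separate route. Appendix 2 drops the limit to target lesions. It has no separate route, because a new lesion acts only through TMTB or through unequivocal progression.

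What is at stake is the event or censoring status, and the date, for irPFS and irDoR in a patient with this relapse pattern. Both are secondary endpoints. If the choice is left open until such a patient appears, it would be made with that patient's outcome in view.

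**Working it through.** The plan states no figure on this point, so there is none to reproduce. The check applies the two rules to the same scans.

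**Rule A** (Appendix 2, Section 4.1): irPD if TMTB ≥ 1.2 × nadir and TMTB − nadir ≥ 5 mm, or if non-target or new non-measurable disease progresses unequivocally. **Rule B** (Section 4.1.1): irPD only for one of the three listed events. Each row is a scan after a confirmed irCR.

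| Finding | Nadir → TMTB (mm) | Rule A | Rule B |
|---|---|---|---|
| New non-nodal lesion, 10 mm | 0 → 10 | irPD | not irPD |
| New non-nodal lesion, 40 mm | 0 → 40 | irPD | not irPD |
| New non-nodal lesion, 20 mm, beside a residual 8 mm node | 8 → 28 | irPD | not irPD |
| New 15 mm node | 0 → 15 | irPD | irPD (item 2) |
| New 15 mm node beside two residual 9 mm nodes | 18 → 33 | irPD | irPD (item 2) |
| New non-measurable disease, unequivocal progression | 0 → 0 | irPD | irPD (item 3) |
| Target lesion reappears at 6 mm | 0 → 6 | irPD | irPD (item 1) |

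The conflict does not depend on how a percentage rise from zero is read. In the third row 28/8 = 3.5, a rise of 250% and 20 mm, and the nodal sum stays at 8 mm, so item 2 is not met. The rules disagree only for the new non-nodal measurable lesion.

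**Effect on one hypothetical patient, on the 8-week scan schedule.** irCR is first seen at week 24 and confirmed at week 32. A new 25 mm lung lesion appears at week 40 and is still present at week 48.

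- Rule A: irPD at week 40, confirmed at week 48. irDoR is 40 − 24 = 16 weeks, an event.
- Rule B with the Section 4.3 carry-forward: no irPD. At week 48 irDoR is 48 − 24 = 24 weeks and still running.

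**How many patients.** Protocol Section 1.2.1.2 reports, for the additional efficacy analysis in February 2018 (the cut-off year given in the Amendment 3 rationale), 7 responders among 95 well-differentiated patients and 1 among 21 GEP-NEC patients. All were PR by BIRC under RECIST 1.1, so there were 0 CR in 95 + 21 = 116. The exact two-sided 95% upper limit is 1 − 0.025^(1/116) = 3.1%. irCR counts are not disclosed. At assumed irCR rates of 1%, 2% and 3%, the expected numbers are 116 × 0.01 = 1.2, 116 × 0.02 = 2.3 and 116 × 0.03 = 3.5 patients. Only those who relapse solely through a new non-nodal measurable lesion would be affected.

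**Two smaller mismatches in the same appendix.**

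- Section 4.1.1 gives irCR at target-lesion level when "all nodal target and new-measurable lesions shrink to less than 10 mm and all non-nodal target lesions have disappeared". It does not clearly require non-nodal new measurable lesions to disappear, as Section 4.1 does.
- The irPD row of Table 4-1 omits the 5 mm minimum. This matters when 20% of nadir is below 5 mm, that is, when nadir is below 5/0.2 = 25 mm. A nadir of 15 mm with 3 mm growth (3/15 = 20%) is irPD by the table but not by the text.

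**The case against.** A reader might infer more: that Appendix 2 keeps any patient who relapses at a new site in irCR, so that irDoR and irPFS are inflated without limit. The documents do not support that, for four reasons.

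- New measurable nodes fall under item 2, and unequivocally progressing new non-measurable disease under item 3.
- Nothing gives the notes in Section 4.1.1 precedence over Section 4.1. Section 4.2 confirms irPD against the Section 4.1 criteria, and a scan with a new measurable lesion cannot meet the irCR definition. What is shown is a contradiction; longer durations follow only if Section 4.1.1 is the text applied.
- Death from any cause is an irPFS event, and death due to the underlying cancer ends irDoR. In the primary analysis durations are also capped by the cut-off: from first consent on 14-Feb-2017 to 10-Aug-2018 is 542 days, about 18 months.
- The primary endpoint (ORR) and key secondary endpoint (DoR) use RECIST 1.1, RECIST 1.1 PFS is reported alongside irPFS, and no hypothesis is tested.

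The smaller mismatches do not add to an inflation argument. The target-level wording sits beneath an overall irCR definition that still requires every lesion to be gone. Omitting the 5 mm minimum would bring irPD forward, which is the opposite direction. It can also be said that the central reading rules are in the independent review charter, which is not among the documents.

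All of this narrows the point. It does not remove it: for one type of scan the appendix gives two incompatible answers, and the SAP does not choose between them.

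**Conclusion.** The contradiction is real and narrow. For a non-nodal measurable lesion first appearing after a confirmed irCR, Section 4.1.1 with Section 4.3 withholds irPD, while Sections 3, 4 and 4.1 assign it. Under the literal Section 4.1.1 reading, irPD is delayed or lost and that patient's irPFS and irDoR are lengthened until a qualifying death or censoring.

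The expected effect on the reported irRECIST results is very small. This rests on the absence of RECIST 1.1 complete responses at the last disclosed analysis and on assumed irCR rates of 1% to 3%; the actual irCR count could differ. It is still worth correcting, because an explicit rule gives the wrong answer if followed and the correction is cheap.

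**What to change.** Before database lock, reconcile Appendix 2 Sections 3, 4, 4.1 (with Table 4-1), 4.1.1 and 4.3 for the derivation of irRECIST endpoints. One way is to state that the Section 4.1.1 restriction applies only to lesions already being followed, and that a new measurable lesion after confirmed irCR is classified by the existing Section 4.1 TMTB rule: 20% and 5 mm over nadir, with the usual confirmation. This keeps both existing criteria and does not duplicate item 2 for nodes.

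In the same edit, align the target-level irCR wording in Section 4.1.1 with the Section 4.1 definition for non-nodal new measurable lesions, and align the irPD row of Table 4-1 with the 5 mm minimum. A pointer in SAP 2.7.1 would make the chosen rule traceable, and the independent review charter should be checked for consistency.

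Under Protocol Section 6.1.5.1, irPD also bears on stopping treatment. There the request is only that the passages be reconciled; no stopping rule is proposed.

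Cost: a few lines and no new data. irPFS or irDoR may become slightly less favourable.
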